5.2 Secondary Outcomes

- 5.2.1 The proportion of SSI using a tertiary closure technique compared to historical controls receiving a secondary wound closure.
- 5.2.2 The length of stay as defined by the time from surgery to discharge as compared to historical controls receiving a secondary wound closure.
- 5.2.3 The proportion of patients that return within 30 days of surgery.
- 5.2.4 The quality of life in patients receiving a tertiary wound closure. It is expected that tertiary closure will be superior to secondary closure. The time to closure with the tertiary approach should be much shorter. It is unknown if wounds closed in a tertiary manner will remain closed. That was our rationale for choosing wound closure at 30 days as the primary endpoint. Differences in quality of life between the two approaches are also unknown. We have submitted an abstract from a chart review of 5 patients who have undergone tertiary closure. We are looking to expand this cohort of patients to generate more quantitative data.

6.0 Analytic Plan

6.1 Sample Size and Power

Twenty patients with a tertiary closure will be recruited (experimental group). The proportion of wound closure within 30 days for these patients will be compared to the proportion from 100 historical controls receiving a secondary wound closure. We anticipate closer to 100% of wound closure in the experimental group and closer to 0% of wound closure in the control group. Assuming the significance level at 0.05 and a two-sided test, we have greater than 90% power to claim that the proportions of wound closure within 30 days are different between the two groups.

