Clean	No hollow viscus entered Primary wound closure No inflammation No breaks in aseptic tech Elective procedure	1 – 3%	
Clean contaminated	Hollow viscus entered but controlled No inflammation Primary wound closure Minor breaks in aseptic tech Bowel prep preop	5-6%	
Contaminated	Uncontrolled spillage from viscus Inflammation apparent Open,traumatic wound Major break in aseptic tech	20 – 25%	
Dirty	Untreated, uncontrolled spillage Pus in op wound Open suppurative wound Severe inflammation	30 – 40%	

Specifically related to gynecologic surgery, hysterectomy would be a clean contaminated or class II wound. Gross spillage from the gastrointestinal tract would be considered a contaminated or class III wound. A perforated viscus or abscess requiring surgery would be considered a dirty/infected or class IV wound. Prophylactic antibiotics are indicated for class II and III wounds; therapeutic antibiotics are necessary for class IV wounds.

Within the group of class II wounds (hysterectomy), there are a subset of patients in which there are factors that increase the risk of SSI above baseline. These include:

- a. Hyperglycemia,
- b. Smoking,
- c. Obesity (BMI \geq 30),
- d. Depth of subcutaneous tissue \geq 3 cm,
- e. Coexistent infection at a remote body site,
- f. Vaginal colonization (bacterial vaginosis),
- g. ASA status > 2,
- h. Immunodeficiency (chronic steroids, chemotherapy), and
- i. MRSA.

Numerous measures have been proved and/or recommended to decrease postoperative infection.

1. Preoperative Measures

- a. Treat remote infections
- b. Clippers if shaving needed
- c. Serum glucose control < 200 mg/dl
- d. Antimicrobial bath/shower
- e. Chlorhexidine abdominal/vaginal prep (70%/4%)
- f. Antibiotic prophylaxis

2. Intraoperative Measures

- a. Surgical technique
- b. Preventing hypothermia
- c. Appropriate re-dosing of prophylactic antibiotics
- d. Prevention of dead space and incisional seromas

Wound management techniques after fascial closure to address reduction in incisional infections especially in high risk class II and class III/IV wounds have included the following:

- Primary closure with subcutaneous drains and possibly incisional vacuum assisted closure device (VAC) for 3-4 days,
- Secondary closure with wound packing and dressing changes 2-3 times daily or VAC placement with changes 2-3 times weekly, and
- Tertiary or delayed primary closure.

Three techniques of wound treatment

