2.0 Objectives

2.1 Primary Objective

2.1.1 To compare the percentage of patients whose wound remained closed on postoperative day #30 after tertiary closure compared to historical controls who underwent secondary wound closure. We are primarily looking at time to wound closure. We will be able to abstract this information from the postoperative clinic visit notes from patients in the "historical control" cohort. We will identify 20 patients with characteristics described in the inclusion criteria of this study who underwent laparotomy with secondary wound closure during the calendar year 2018.

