3.2 Exclusion Criteria

- 3.2.1 Pregnancy
- 3.2.2 Allergy to triclosan
- 3.2.3 Patients undergoing HIPEC

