6.3 Analysis of Primary Outcome

The chi-squared test will be used to compare the proportions of wound closure within 30 days between the experimental group (i.e., patients receiving a tertiary wound closure) and the historical control group (i.e., patients receiving a secondary wound closure). Logistic regression models will be used when confounding variables such as age will be adjusted. Wound closure status is the outcome measure. Experimental group is the covariate of interest.

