6.4 Analysis of Secondary Outcomes

6.4.1 The analysis approach for comparing the proportion of acute and chronic wound infection between the two groups is the same as that specified in 6.3.

6.4.2 The distribution of length of stay will be examined and transformed if needed. To compare the length of stay between the two groups, the 2-sample t-test will be used if the length of stay is normally distributed and the Wilcoxon rank sum test will be used if it is not normally distributed. To adjust for confounding variables, a linear regression model will be used if the length of stay is normally distributed and a negative binomial model will be used if it is not normally distributed.

6.4.3 The analysis approach for comparing the proportion of patients that return within 30 days of surgery between the two groups is the same as that specified in 6.3.

6.4.4 Descriptive statistics, including mean, standard deviation, median, and interquartile range, will be calculated to describe the quality of life in patients receiving a tertiary wound closure,

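### The historical control group is 20 patients in Section 2.1.1 and 100 in Section 6.1, and nothing shows which number governs

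*Combined protocol and SAP*

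**What the plan says.** Section 2.1.1 (primary objective) defines the comparator by count and by year: "We will identify 20 patients with characteristics described in the inclusion criteria of this study who underwent laparotomy with secondary wound closure", in calendar year 2018. Their closure data are to come from postoperative clinic notes.

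Section 6.1 recruits 20 tertiary-closure patients, whose 30-day closure proportion is to be "compared to the proportion from 100 historical controls receiving a secondary wound closure". It gives no year or source for the 100. The assumption behind the power statement is: "We anticipate closer to 100% of wound closure in the experimental group and closer to 0% of wound closure in the control group". From this, with two-sided alpha of 0.05, it claims more than 90% power.

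Section 6.3 names the test: "The chi-squared test will be used to compare the proportions of wound closure within 30 days between the experimental group" and the historical controls, with logistic regression for adjustment. Section 6.4 applies the same approach to infection and 30-day return, and a t-test or rank-sum test to length of stay. Sections 2.2, 5.1, 5.2, 6.3 and 6.4 refer to the controls without a number. The 20 in Section 6.5 is accrual of enrolled patients, so it does not settle the control count.

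**The concern.** The two sections describe the same control group for the same primary comparison. One gives a 1:1 design and the other 5:1. Nothing says that the 20 are a subset of the 100 or that either number has been superseded, so two people following the two sections would build different datasets.

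Three things are at stake:

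- **Precision.** The control closure rate and all two-group comparisons in Section 6.4 depend on the control count, and Section 6 states no power or precision for the secondary outcomes.
- **Reproducibility.** Section 6.1 gives no exact closure proportions, so its power cannot be recomputed exactly for whichever number is kept.
- **Timing.** The control outcomes are already in the charts. With the number open, the comparator's size could be settled after outcomes are seen.

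A related gap exists at either number. Section 2.1.1 points to the inclusion criteria but gives no rule for choosing among eligible charts if there are more than needed.

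**Working it through.** **Inputs from the documents.** Enrolled n1 = 20 (6.1); controls n0 = 20 (2.1.1) or 100 (6.1); two-sided alpha 0.05 (6.1); chi-squared test (6.3). **Assumed**, because the plan gives no exact values: closure proportions p1 (enrolled) and p0 (control), varied from 90/10 to 70/30.

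**1. The plan's own figure, then the alternative.** Exact power is the sum of Bin(a; 20, p1) × Bin(b; n0, p0) over all outcomes (a, b) for which the uncorrected chi-squared test gives p ≤ 0.05.

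| p1 / p0 | 100 controls | 20 controls |
|---|---|---|
| 90% / 10% | about 100% | about 100% |
| 80% / 20% | about 100% | 98.2% |
| 75% / 25% | 99.2% | 90.1% |
| 70% / 30% | 92.8% | 71.3% |

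The claim of more than 90% is reproduced with 100 controls. With 20 it holds down to 75/25. Section 6.3 does not say whether a continuity correction applies. With the correction, or with Fisher's exact test, power with 20 controls is about 96% at 80/20 and 82% to 83% at 75/25.

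**2. Closure needed in the enrolled group for 90% power if p0 = 10%** (search in steps of 0.01): 55% with 20 controls (power 0.907) and 42% with 100 (power 0.913). Both are far below what Section 6.1 anticipates.

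**3. Precision of the control rate if no control wound is closed.** The Clopper-Pearson upper 95% limit is 1 − 0.025^(1/n).
- n = 20: 16.8%
- n = 100: 3.6%

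**4. Secondary comparisons, common rate or SD.** The standard error is proportional to √(1/n1 + 1/n0).
- 20 v 20: √(0.05 + 0.05) = 0.3162
- 20 v 100: √(0.05 + 0.01) = 0.2449
- Ratio: 0.3162 / 0.2449 = 1.29

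**5. Infection, for illustration.** The plan gives no expected infection rate for either group. I assumed a common rate p between 5% and 40%, the span of the clean-contaminated, contaminated and dirty rows in the Section 1.0 wound-class table. The approximate 95% half-width is 1.96 × √(p(1 − p)) × √(1/n1 + 1/n0).

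| p | 20 controls | 100 controls |
|---|---|---|
| 5% | 13.5 points | 10.5 points |
| 25% | 26.8 points | 20.8 points |
| 40% | 30.4 points | 23.5 points |

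**6. Length of stay.** By two-sample t-test, the difference detectable with 80% power is 0.91 SD (20 v 20) or 0.69 SD (20 v 100).

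**The case against.** The strongest reply is that nothing in the primary analysis changes. The power claim is true at either count under any fair reading of the anticipated rates. The 70/30 row, the only one in the table that falls below 90%, is not such a reading. This stands: the point is an internal inconsistency and not a wrong calculation, and restating the power would tidy Section 6.1 without altering its conclusion.

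The infection half-widths can also be challenged. The Section 1.0 table is general background, and its clean-contaminated row presupposes primary closure, which neither group has. Only high-risk class II wounds are eligible, so 5% is probably too low for them. The normal approximation is rough when about one event is expected in 20 patients. This also stands, and those figures are illustrative only. The ratio of 1.29 holds for any common rate or SD.

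The missing selection rule is a separate gap, and Section 2.1.1 does give a year, a procedure, a closure type and the inclusion criteria. Nothing suggests that anyone intends to choose controls after seeing outcomes. Both remarks are fair. The rule is included because it belongs in the same sentence that must be corrected, and because the possibility costs little to close.

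None of this reconciles 20 with 100.

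**Conclusion.** The concern holds and should be fixed. The plan gives two sizes for one control group, and the documents do not show which is intended. The primary power statement is safe with either, provided closure is near the anticipated extremes. The practical effect is on the control-rate estimate (upper limit 16.8% v 3.6% if no control wound is closed) and on the secondary comparisons, where the standard error is 1.29 times larger with 20 controls at a common rate or SD. The closure proportions and infection rates in the working are assumptions. The contradiction itself depends on neither.

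**What to change.** Before any control outcomes are abstracted:

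1. State one control number, the one that can actually be obtained, in both Section 2.1.1 and Section 6.1, with its source period.
2. Restate the power in Section 6.1 for that number, with explicit assumed closure proportions.
3. Add an outcome-blind selection rule: either all eligible secondary-closure laparotomies in the period, or consecutive cases by date until the number is reached. Apply Section 3.1 and the Section 3.2 exclusions relevant to controls, namely pregnancy and "Patients undergoing HIPEC".

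**Cost.** The change is to protocol wording and needs no extra enrolled patients. Keeping 100 means up to 100 − 20 = 80 more chart abstractions. If 2018 alone does not yield 100 eligible cases, it also means a longer source period, with more scope for differences over calendar time. Keeping 20 means accepting the less precise secondary comparisons, which Section 6 should then state.

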6.2 Interim Analysis

6.2.1 After five patients an interim analysis will be performed to assess safety outcome of the trial. If all five patients are unhealthy the protocol will be suspended until independent review of outcomes. (an unhealthy patient is one with either a wound or systemic infection. A wound infection is an incision with skin erythema, purulent drainage, nonviable or necrotic subcutaneous tissue or a positive wound culture. Systemic infection is defined as a SIRS response with additional evidence of wound infection as the most likely source of the systemic infection). Amendments or closure will be made per the recommendation.

6.3 Analysis of Primary Outcome

The chi-squared test will be used to compare the proportions of wound closure within 30 days between the experimental group (i.e., patients receiving a tertiary wound closure) and the historical control group (i.e., patients receiving a secondary wound closure). Logistic regression models will be used when confounding variables such as age will be adjusted. Wound closure status is the outcome measure. Experimental group is the covariate of interest.

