5.0 Outcome Measures

5.1 Primary Outcomes

- 5.1.1 The percentage of patients whose wound is closed on postoperative day # 30 after tertiary wound closure compared to historical controls who underwent secondary wound closure.

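### Sections 6.1 and 6.3 power and test closure within 30 days, whereas the primary outcome in 5.1.1 is the wound being closed on postoperative day 30

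*Combined protocol and SAP*

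**What the plan says.** The primary endpoint is worded differently in three parts of the combined protocol and SAP.

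- Section 2.1.1 (primary objective): "To compare the percentage of patients whose wound remained closed on postoperative day #30 after tertiary closure". The same paragraph adds "We are primarily looking at time to wound closure".
- Section 5.1.1 (primary outcome): "The percentage of patients whose wound is closed on postoperative day # 30 after tertiary wound closure".
- Section 6.1 (sample size): "The proportion of wound closure within 30 days for these patients will be compared to the proportion from 100 historical controls". Section 6.3 (primary analysis) uses the same within-30-days variable for the chi-squared test, which is to "compare the proportions of wound closure within 30 days between the experimental group (i.e., patients receiving a tertiary wound closure" and the historical controls. It then says of the logistic model "Wound closure status is the outcome measure", with no time point.

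Section 5.2.4 gives the reason for the endpoint: whether tertiary-closed wounds will stay closed is not known. Under 4.3.3 the skin edges are brought together at the bedside on day 4-7. Section 10.1.1 expects the incision to be re-opened if a deeper infection occurs. The wound form (Appendix F) asks about dehiscence and its date (item 2), the date of closure (item 5) and closure on POD 30 (item 6). Section 6.3 does not say which item supplies the primary variable.

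**The concern.** Status on a given day and an event by a given day are different variables. In this trial they separate in exactly the patients of interest: those whose wound was approximated on day 4-7, re-opened, and was still open on POD 30. The Section 6 wording, taken literally, counts such a patient as a success; 5.1.1 counts her as a failure. An analysis built on the literal wording would credit the study procedure itself and could not show a failure of durability.

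The literal rule would apply to both groups, but its effect would fall mainly on the experimental group, because 6.1 anticipates "closer to 0% of wound closure in the control group". What is at stake is the size and meaning of the reported success rate, not whether the test reaches significance.

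**Working it through.** **1. The plan's own power.** Inputs from 6.1: 20 experimental patients, 100 controls, two-sided 0.05, proportions near 100% and near 0%. Section 2.1.1 gives 20 controls, so both sizes were run. No exact proportions are stated; 90% and 10% are assumed here as a cautious version.

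Formula: power = Φ[(|p1 − p2| − 1.96·SE0)/SE1], where SE0 = √[p(1 − p)(1/n1 + 1/n2)] with p the pooled proportion, and SE1 = √[p1(1 − p1)/n1 + p2(1 − p2)/n2].

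- 100 controls: p = (18 + 10)/120 = 0.233; SE0 = 0.1036; SE1 = 0.0735; (0.8 − 0.203)/0.0735 = 8.1, so power exceeds 99.9%.
- 20 controls: p = 0.5; SE0 = 0.158; SE1 = 0.0949; (0.8 − 0.310)/0.0949 = 5.2, so power exceeds 99.9%.

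The claim of more than 90% reproduces. Exact enumeration with uncorrected chi-squared, continuity-corrected chi-squared and Fisher's test agrees.

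**2. The wordings applied to the same wound.**

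| Course of a tertiary wound | 6.1/6.3, literal | 5.1.1 |
|---|---|---|
| Approximated day 4-7, stays closed | closed | closed |
| Approximated, re-opens, open on POD 30 | closed | not closed |
| Approximated, re-opens, healed again by POD 30 | closed | closed |
| Never closed by POD 30 | not closed | not closed |

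Only the second row separates 6.1/6.3 from 5.1.1. The third row separates 5.1.1 from the remained-closed wording of 2.1.1, but it should be uncommon: 6.1 expects almost no wound left open from surgery to close by day 30, and a wound re-opened after day 4-7 has less time.

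**3. Effect on the reported rate.** Assumptions: all 20 wounds are approximated, and k of them are open on POD 30. The documents give no value for k. Intervals are exact (Clopper-Pearson) 95%; for 20/20 the lower limit is 0.025^(1/20) = 0.832.

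| k | Within 30 days, literal | Closed on POD 30 |
|---|---|---|
| 0 | 20/20 (83-100%) | 20/20 (83-100%) |
| 2 | 20/20 (83-100%) | 18/20 = 90% (68-99%) |
| 4 | 20/20 (83-100%) | 16/20 = 80% (56-94%) |
| 6 | 20/20 (83-100%) | 14/20 = 70% (46-88%) |

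**4. What is known about k.** The six-patient series in Section 1.0 had no wound complications at sixty days. The exact upper limit for 0/6 is 1 − 0.025^(1/6) = 0.459, so the interval is 0-46%. The rate is unknown; it has not been shown to be high.

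**5. Power on the 5.1.1 outcome.** At k = 6 (70%) against an assumed 10% in controls, exact power with 100 controls exceeds 99.9%. With 20 controls it is 99.0% (uncorrected), 97.3% (continuity-corrected) and 97.9% (Fisher).

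**6. Whether POD 30 can be observed.** The activities table in 4.2 puts the wound assessment at 4 weeks ± 5 days: 28 − 5 = 23 to 28 + 5 = 33. Of these 11 permitted days, 7 (days 23 to 29) precede POD 30. The next scheduled assessment is at 3 months. For controls, 2.1.1 relies on clinic notes: "We will be able to abstract this information from the postoperative clinic visit notes".

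**The case against.** The strongest reply is that within 30 days is shorthand. Section 6.3 is headed as the analysis of the primary outcome, and that outcome is defined in 5.1.1 as status on POD 30. Section 6.3 calls its variable a closure status. Section 5.2.4 describes the endpoint as closure at 30 days and gives durability as the reason. Appendix F item 6 is a yes/no field for exactly that status. An analyst would have to disregard all of this to score the day 4-7 procedure as success.

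Most of that stands. A reader might infer that the plan intends to count every approximated wound as a success, or that the documents leave the two readings evenly balanced. Neither inference is supported: the weight of the text favours POD 30 status. The reply does not remove the mismatch, though. The within-30-days phrase is used for wound closure three times (twice in 6.1, once in 6.3), the closure date in Appendix F item 5 would allow that variable to be built, and 6.3 names no source item.

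It is also fair to say that every re-opening count above is assumed, and that the only data in the documents show none.

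**Conclusion.** The concern holds as a mismatch between the defined outcome and the variable that Section 6 powers and tests. It is probably loose drafting, and it is worth correcting because the literal Section 6 variable could not answer the question the endpoint was chosen for.

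The effect on the result cannot be determined from the documents. It is zero if no wound re-opens. It is 10 to 30 percentage points in the experimental group if 2 to 6 of 20 wounds are open on POD 30, assuming all 20 were approximated.

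Two stronger conclusions should not be drawn. The sample size is not undermined: power stays above 90% under either definition at the anticipated rates, and at 70% against 10%. Nor do the documents show that re-opening is frequent; they show only that it is foreseen and that its rate is not known.

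**What to change.** 1. In 6.1 and 6.3, replace closure within 30 days with wound closed on POD 30, as in 5.1.1. State that a wound open on POD 30 counts as not closed, whether it never closed or closed and re-opened.
2. In 2.1.1, use the same wording and list time to closure as a secondary or descriptive outcome.
3. Take the outcome from Appendix F item 6, checked against items 2 and 5. State in advance how POD 30 status is assigned when the 4-week visit falls before day 30, for example from the closure and dehiscence dates recorded at the next contact.
4. Apply the same rule to the historical controls, and report the number with undeterminable POD 30 status in each group.
5. A wound that re-opened and healed again by POD 30 counts as closed under 5.1.1. Reporting the number of such wounds is enough.

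Cost: wording changes in 2.1.1, 6.1 and 6.3 and one assignment rule. No extra patients, visits or procedures are needed. The downsides are that the success rate may be slightly less favourable, and that POD 30 status may be undeterminable for some patients in either group: experimental patients seen before day 30, and controls whose clinic notes are sparse.

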Six consecutive patients undergoing gynecologic abdominal surgery had tertiary closure. The mean patient age and BMI were 51 and 28, respectively. Two patients had surgery for benign conditions and four for malignancy. Two of the six wounds were class IV (abscess) and the other four wounds were class III (GI contamination). The mean operative duration was 5.5 hours and the median length of stay was 4 days. At sixty days, no SSI or other wound complications were identified.

Conclusions

Tertiary closure of high-risk gynecological abdominal wounds is safe and feasible. Based on this data, we have designed a larger trial comparing outcomes of tertiary closure to secondary closure for high-risk patients undergoing gynecologic abdominal surgery.

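### The only adjusted analysis in section 6.3 is logistic regression, which has no finite odds ratio if a cell is empty, as section 6.1's expected rates make plausible

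*Combined protocol and SAP*

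**What the plan says.** Section 6.3 compares 30-day wound closure between the tertiary group and historical controls with a chi-squared test. For adjustment it says only: "Logistic regression models will be used when confounding variables such as age will be adjusted". Closure status is the outcome and group is the term of interest. Neither section 6 nor any other part of the document mentions a penalised or exact fit, standardisation, matching, or what to do if a cell is empty.

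Section 6.1 plans 20 tertiary patients against 100 controls and states: "We anticipate closer to 100% of wound closure in the experimental group and closer to 0% of wound closure in the control group". It gives no exact rates. Section 5.2 is more cautious: "It is unknown if wounds closed in a tertiary manner will remain closed".

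Section 2.1.1 has a different control count: "We will identify 20 patients with characteristics described in the inclusion criteria of this study". That conflict is a separate matter, but both counts are carried through below.

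Section 6.4.1 says that the approach for "comparing the proportion of acute and chronic wound infection between the two groups is the same as that specified in 6.3", and section 6.4.3 does the same for return within 30 days.

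**The concern.** The plan's single adjusted method is paired with the data pattern in which its usual form fails. If every wound in one group has the same outcome, the likelihood keeps rising as the group coefficient grows. Maximum likelihood then gives no finite odds ratio, and the software output depends on when iteration stops. A Wald p-value near 1 could be printed beside an overwhelming chi-squared result.

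This matters because the groups are not randomised. Section 2.1.1 restricts controls to patients who meet the inclusion criteria, but section 3.1 admits high-risk class II to class IV wounds and both benign and malignant disease. Regression is the only statistical control of confounding in section 6. If it fails, a replacement has to be picked with the data in view.

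**Working it through.** **Inputs.** 20 tertiary patients (6.1); 100 controls (6.1) or 20 (2.1.1); two-sided 5% level and power above 90% (6.1). Closure rates are assumed, because 6.1 says only that they will be close to the extremes.

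**The plan's own figure.** Power with 20 v 100 is about 1.00 at 99% v 1%, 95% v 5% and 90% v 10%, 0.9999 at 80% v 20%, and 0.93 at 70% v 30%. With 20 v 20 it is 0.99 at 80% v 20%. The power statement is reproduced for any rates near those anticipated.

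**What maximum likelihood does.** Fits with group and one simulated covariate standing in for age, 20 v 100, stopped at 10, 25 and 50 iterations:

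| Closed, tertiary v control | Group log-OR | Wald p |
|---|---|---|
| 20/20 v 0/100 | 23.1, 53.1, 74.7 | 0.63, 0.9995, 1.0 |
| 20/20 v 5/100 | 14.7, 29.7, 40.4 | 0.73, 0.9997, 1.0 |
| 19/20 v 0/100 | 14.7, 29.7, 40.3 | 0.45, 0.9993, 1.0 |
| 19/20 v 5/100 (no zero cell) | 6.09 throughout, SE 1.18 | below 0.0001 |

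One empty cell is enough. At 20/20 v 0/100 the standard error goes from 48 to 87,329 to about 16 million. The Pearson chi-squared for the same table is 120.0.

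**How likely a zero cell is.** With tertiary rate pE, control rate pC and n controls:

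P = 1 − (1 − pE^20 − (1−pE)^20) × (1 − (1−pC)^n − pC^n)

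At 95% v 5%, 0.95^20 = 0.3585 and 0.95^100 = 0.0059, and the other two terms are negligible. So P = 1 − 0.6415 × 0.9941 = 0.362 with 100 controls, and 1 − 0.6415² = 0.588 with 20.

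| Assumed rates | 100 controls | 20 controls | 20/20 closed in tertiary arm alone |
|---|---|---|---|
| 99% v 1% | 88% | 97% | 82% |
| 98% v 2% | 71% | 89% | 67% |
| 95% v 5% | 36% | 59% | 36% |
| 90% v 10% | 12% | 23% | 12% |
| 85% v 15% | 4% | 8% | 4% |
| 80% v 20% | 1% | 2% | 1% |

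With 100 controls and rates of 95% v 5% or less extreme, almost all of the risk is a full 20/20 in the tertiary arm.

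**What Firth gives.** Without covariates, Firth's estimate equals adding 0.5 to each cell. At 20/20 v 0/100 the OR is 20.5 × 100.5 / (0.5 × 0.5) = 8241, log-OR 9.0 (profile 95% CI 6.0 to 14.8). At 19/20 v 0/100 it is 19.5 × 100.5 / (1.5 × 0.5) = 2613, log-OR 7.9 (5.4 to 12.9).

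With a simulated standard-normal age, independent of group and outcome, 300 draws per table:

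| Table | Median log-OR | Range |
|---|---|---|
| 20/20 v 0/100 | 8.3 | 8.2 to 9.6 |
| 19/20 v 0/100 | 7.7 | 7.3 to 13.7 |
| 20/20 v 1/100 | 7.8 | 7.4 to 14.4 |
| 18/20 v 3/100 | 5.3 | 5.1 to 6.4 |

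Call a patient discordant if the outcome is the opposite of that expected for the group. With one discordant patient, the adjusted estimate depends heavily on that patient's age. In 30 further draws for each of 20/20 v 0/100, 19/20 v 0/100, 20/20 v 1/100 and 19/20 v 1/100, the lower profile limit was never below 4.4. The upper limit reached 104 at 19/20 v 0/100.

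**Secondary outcomes.** For infection at a common rate r with 100 controls, P(no infection in at least one arm) = 1 − (1 − (1−r)^20)(1 − (1−r)^100). This is 36% at r = 5%, 29% at 6%, 1.2% at 20% and 0.3% at 25%. The section 1.0 table gives 5–6% for clean-contaminated wounds and 20–25% for contaminated ones. Section 1.0 also says of class II that "there are a subset of patients in which there are factors that increase the risk of SSI above baseline", and all six pilot wounds were class III or IV, so the lower probabilities fit this population better. No 30-day return rate is given.

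**The case against.** The strongest reply is that the adjusted model is supporting. Chi-squared is the primary comparison, it survives an empty cell, and a likelihood-ratio test can still be formed from the logistic model. Section 6.3 promises neither an odds ratio nor a Wald test, and a penalised fit is itself a logistic model. All of that is true, and it limits the weight of the point. It does not close the gap. Maximum likelihood is the usual default, 6.3 does not name the likelihood-ratio test, and leaving the estimator open is the defect.

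The probabilities rest on assumed rates and run from 88% to 1% with 100 controls. That stands: the problem is likely only if the plan's own expectation is close to right.

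The remedy is also partial. Firth's estimate can be finite yet barely informative with one discordant patient. The simulated age carries no confounding, so the simulation cannot show that confounding control improves. The open covariate list in 6.3 leaves further post-hoc choice that naming an estimator does not remove. These points stand as limits on what the fix achieves.

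Finally, a fallback used only when a cell is empty would avoid shrinkage elsewhere. It would, but the method would then depend on the data. Using one method throughout avoids that switch at modest cost.

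**Conclusion.** The gap is real and should be corrected. If a zero cell occurs, section 6.3 followed by ordinary maximum likelihood yields no usable adjusted estimate, interval or Wald p-value, and the plan names nothing to use instead. The size is conditional on the true rates, which the documents do not give. With 100 controls a zero cell is more likely than not at 98% v 2% or beyond, about one in three at 95% v 5%, and rare at 80% v 20%. It is more likely at each of these rate pairs if the control count is 20.

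The primary chi-squared test, the power claim and the direction of the conclusion are not threatened. The extension to infection is minor at the rates that fit this population.

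**What to change.** In 6.3, name Firth-penalised logistic regression as the single method for the adjusted group effect, whether or not a cell is empty. Pair it with a profile penalised-likelihood 95% interval and a penalised likelihood-ratio test. Keep chi-squared as the unadjusted test. State that the adjusted estimate is always reported with its interval and that, when at most one patient is discordant, it is read as limited control of confounding. Carry the same wording into 6.4.1 and 6.4.3, for consistency only.

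The cost is a change of SAP wording and the use of standard software. The statistical price is shrinkage where cells are sparse, shown here without covariates:

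| Table | ML odds ratio | Firth odds ratio | Reduction |
|---|---|---|---|
| 19/20 v 1/100 | 19×99/(1×1) = 1881 | 19.5×99.5/(1.5×1.5) = 862 | 54% |
| 18/20 v 3/100 | 18×97/(2×3) = 291 | 18.5×97.5/(2.5×3.5) = 206 | 29% |
| 17/20 v 10/100 | 17×90/(3×10) = 51 | 17.5×90.5/(3.5×10.5) = 43 | 16% |
| 16/20 v 20/100 | 16×80/(4×20) = 16 | 16.5×80.5/(4.5×20.5) = 14.4 | 10% |

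The conclusion does not change in any of these. At 19/20 v 1/100, for instance, the Firth log-OR is 6.76 (95% CI 4.8 to 9.6).
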